7.4 Withdrawal of Subjects

A subject may withdraw from the study at any time at his/her own request or may be withdrawn at any time at the discretion of the Investigator for safety, behavioral, or administrative reasons.

Reasons for withdrawal (subjects who refuse to return for any remaining study visits) or discontinuation (subjects who prematurely stop the treatment) at any time during the study may include, but are not limited, to the following:

- 1. Withdrawal of subject consent.
- 2. Investigator determines that withdrawal from the study is in the best interest of the subject.
- 3. Major protocol violation (i.e., circumstances where confounding conditions make it impossible to derive sound scientific or medical conclusions from the primary endpoint data generated on a subject).
- 4. Any condition, injury, or disease that becomes apparent during the study and necessitates the termination of the subject from the study.
- 5. The development of an elevated temperature is not a cause for withdrawal of HU6 alone. Should a subject develop a temperature > 100°F, they should be instructed to repeat the measurement approximately 15 minutes later. If the temperature continues to be elevated, the subject should be instructed to contact the investigational site to be evaluated by the investigator. They should not take HU6 nor any anti-pyretic (acetaminophen, aspirin, nonsteroidal anti-inflammatory drugs) prior to evaluation by the investigator. The investigator should assess the subject medically to ascertain the underlying cause of the elevated temperature. Appropriate laboratory tests, including those for COVID-19 or influenza, may be warranted to provide a diagnosis.
 - a) Should the investigator be unable to identify the cause for the elevated temperature, but the subject's body temperature has returned to normal, dosing with HU6 may be restarted based on the medical judgment of the investigator and in discussions with the medical monitor. Appropriate follow-up should take place once dosing re-starts.

- b) Subjects with persistent temperature elevations after HU6 has been stopped for 3 days may be discontinued from the study to allow appropriate medical care, as medically indicated. Restarting dosing with HU6 in subjects who have not taken the drug for greater than 4 days should be discussed with the medical monitor, as their participation in the study will be discontinued.
- 6. Increased liver function tests will be evaluated in accordance with the Consensus guidelines for best practices for the detection, assessment, and management of suspected acute drug-induced liver injury (DILI) during clinical trial in patients with nonalcoholic steatohepatitis which are applicable to the subjects being enrolled in this trial (Regev et al., 2018). Please see Appendix C for a table from that Consensus that shows the algorithm for monitoring and managing of hepatocellular DILI in phase 2-3 NASH clinical trials in patients with normal or elevated baseline ALT, as well as the listing of the Consensus and Recommendations.
- 7. Administrative reason (e.g., termination of the clinical study by a Regulatory Agency or the Sponsor).
- 8. Lost to follow-up.
- 9. Pregnancy.

7.4.1 Follow-up Procedures for Subjects Who Withdraw Prematurely

Subjects not completing the entire study should be fully evaluated when possible. All withdrawn subjects will be asked to report to the clinic for the Early Termination Visit within 2 weeks after their last dose of the study drug.

Subjects with ongoing AEs or AEs believed to be at least possibly related to study medication will continue to be followed until resolution or for 30 days as warranted by the nature of the AE.

The Investigator must make every attempt to follow-up on subjects who have withdrawn for any reason. When a subject is "lost to follow-up" (i.e., fails to return for study visits), a reasonable effort (3 documented phone calls or 2 phone calls and 2 text messages, on separate occasions, and a follow-up letter sent by registered mail) should be made to contact him/her to determine a reason for the failure to return. If the subject cannot be reached, they should be identified as "lost to follow-up" in the eCRF.

7.4.2 Procedures for Replacing Subjects Who Withdraw Prematurely

A randomized subject who withdraws prior to first dose of study drug may be replaced after consultation with the Sponsor. This subject will be given the same treatment assignment (by the unblinded statistician) as the withdrawn subject. A randomized subject who withdraws from the study after initiation of study drug dosing will not be replaced.

8 TREATMENT PLAN AND METHODS

Study procedures should be completed as designated in the Schedule of Assessments (Section 8.1). However, if a participant is unable to attend a visit within a specified window, the Investigator (or qualified designee) should discuss appropriate scheduling with the Sponsor's Medical Monitor.

Blood samples for HU6, DNP, and M1 PK are required for analysis of parameters and these samples should be collected as close to the protocol-defined times for sample collection as possible.

Whenever 12-lead ECGs, routine vital sign measurements, and blood draws are scheduled for the same time, it is preferable (but not required) that these assessments occur in the following order: 12-lead ECGs, vital signs, and blood draws. The timing of the assessments should allow the blood draws to occur at the approximate nominal time. The actual date and time should be recorded for all procedures and the Investigator should make every effort to perform procedures at the nominal dates and times. However, unscheduled procedures required for the evaluation of safety concerns take precedence over all scheduled routine procedures.

8.1 Schedule of Assessments

	Screening ^a	ng ^a Treatment Visits up											
	Visit 1	Vis	sit 2	Visit 3	Visit 4	Visit 5	Visit 6	Visit 7	Visit 8	Visit 9 ^b	Visit 10	10 Visit	
Activity/Day	Day-45 to - 3	Day 1: Predose	Day 1: Postdose	Day 2	Day 7	Day 14	Day 28	Day 42	Day 49	Day 61 ^b	Day 73	< 28 days of dosing	≥ 28 days of dosing
Visit Window					±1	±1	±4	±4	±2	varies ^b	±2		
Informed Consent	Х												
Inclusion / Exclusion Criteria	х	Х											
Medical History	х	Х											
Alcohol use assessment	Х												
Blood PEth Test	Х						Х						
TSH and T4	Х												
Serum triglycerides	Х												
HbA _{1c}	Х									Х		Х	х
Fibroscan	Х									Х		Х	Х
Demographics	Х												
eGFR (CKD-EPI)	Х												
Coagulation (INR)	Х												
Serology: HIV, HBsAg, HCV Ab	Х												
Urine Drug	Х	Х					Х			Х			
Urine Pregnancy test (female only)	Х	х			х	х	х	х		Х	Х	Х	Х
Laboratory U/A (dipstick)	х	х					х			Х	х	Х	Х
Hematology Panel (CBC)	х	х					х			Х	Х	Х	Х
Serum chemistry (includes LFTs)	х	Х					х			Х	Х	Х	Х

RIV-HU6-203 Version 1.0

	Screening ^a				Treatme	nt Visits					Follow- up		
	Visit 1	Vi	sit 2	Visit 3	Visit 4	Visit 5	Visit 6	Visit 7	Visit 8	Visit 9 ^b	Visit 10		ermination /isit
Activity/Day	Day-45 to - 3	Day 1: Predose	Day 1: Postdose	Day 2	Day 7	Day 14	Day 28	Day 42	Day 49	Day 61 ^b	Day 73	< 28 days of dosing	≥ 28 days of dosing
Visit Window					±1	±1	±4	±4	±2	varies ^b	±2		
Ophthalmologic exam	Х									Х			Х
Vital signs ^c and weight (InBody scale)	х	х	х	х	x	х	х	х	х	х	х	х	х
12-lead ECG	х	Х			х	Х	х	х		Х	Х	Х	х
Concomitant medications	Х	Х	Х	Х	х	х	х	х	Х	Х	Х	Х	Х
Adverse events	Х	Х	х	Х	х	х	х	х	Х	Х	Х	Х	Х
MRI/MRI-PDFF	Xď									Х			Х
Complete physical (includes neuro exam: muscle strength)	х									Х			х
Targeted physical (includes neuro exam: muscle strength)		х				х	х	х			х	х	
Glycated Albumin		х				х	х	х		Х		Х	Х
hs-CRP		Х					Х			Х			Х
Lipid Panel (HDL, LDL, VLDL, FFA, cholesterol, triglycerides)		Х					х			х			Х
ApoB and Lp(a)		Х					х			Х			Х
HOMA-IR: glucose, insulin, and C- peptide (3 draws 5 minutes apart)		х					х			х			Х
OWLiver (Metabolomics)		Х					х			Х			х
OWL (Lipidomics)		Х					х			Х			х
Proteomic Profile (SomaScan)		Х					х			Х			х

	Screening ^a Visit 1	Vi	sit 2	Visit 3	Treatme Visit 4	nt Visits Visit 5	Visit 6	Visit	Visit 8	Visit 9 ^b	Follow- up Visit 10	up /isit Early Termination		
Activity/Day	Day-45 to -	Day 1: Predose	Day 1: Postdose	Day 2	Day 7	Day 14	Day 28	Day 42	Day 49	Day 61 ^b	Day 73	< 28 days of dosing	/isit ≥ 28 days of dosing	
Visit Window					±1	±1	±4	±4	±2	varies ^b	±2			
Enhanced Liver Fibrosis Assay (ELF)		х								х			х	
Exploratory biomarker (Serum sample)		Х					х			х			Х	
Exploratory biomarker (Plasma sample)		Х					х			Х			X	
Plasma sampling for PK ^e		Х	х	Х	Х	Х	Х	Х		Х	Х	Х	Х	
Dispense study drug				Х	Х	Х	Х	Х	Х					
Administer study drug		Х		Х	Х	Х	Х	Х	Х	Х				
Dispense Daily Log (dosing, temperature, diet)				х	Х	Х	х	Х	Х					
Collect Daily Log (dosing, temperature, diet)					Х	х	х	х	Х	Х		Х	Х	

- a. Subjects will be screened over a 45 day period to determine their eligibility based on specific history, physical, laboratory and imaging evaluations as per the Schedule of Assessments. Due to scheduling of the procedures, multiple visits will likely be necessary to complete the screening process. However, if all screening assessments and procedures can be completed within 30 days of first dose, then a single screening visit is permissible.
- b. Visit 9 may be split into a series of visits to complete all assessments. Please see Section 8.2.9. Administering study drug: if the visit occurs on Day 61. For those subjects whose visit occurs on Day 62, the last dose should be taken on Day 61, with no drug administered on Day 62.
- c. Vital signs (body temperature, systolic and diastolic blood pressure, heart rate, and respiration rate) conducted twice (predose and prior to discharge) on Days 1, 14, and 28. Only predose vital sign assessments on other Treatment Visit Days.
- d. By exception, MRI must be 30 days prior to Day 1 dosing (see Section 8.2.1)
- e. PK Sampling: On Day 1, 14, and 28: predose, and approximately 2, 4, and 6 hours. On Days 2, 7, 42, and 61: predose sample. One sample during Visit 10 or Early Termination.

8.2 Study Specific Procedures

Below is a list of procedures per visit. The description for each assessment can be found in the specific sections.

8.2.1 Screening

Subjects will be screened over a 45 day period to determine their eligibility based on specific history, physical, laboratory and imaging evaluations as per the Schedule of Assessments. Due to scheduling of the procedures, multiple visits will likely be necessary to complete the screening process. The screening assessments are outlined in Section 8.2.1.1 below. However, a single screening visit or amended screening visit schedule may be possible as follows:

- If all screening assessments and procedures can be completed within 30 days of first dose, then a single screening visit is permissible.
- The baseline MRI must be conducted within 30 days of Day 1 dosing.
- The Investigator may repeat vital signs, ECGs and laboratory tests once to verify results as based on clinical judgment at the time of the subject screening evaluation.

8.2.1.1 Visit 1 / Screening – (-45 days to -3 days)

Screening assessments will occur within -45 to -3 days prior to Visit 2 / Day 1.

The following procedures will be performed:

- Obtain signed Informed Consent Form.
- Measure and record vital signs and InBody Scale for weight (Section 11.3).
- Evaluate subject eligibility against study inclusion/exclusion criteria.
- Record demographics and ethnicity.
- Obtain medical history including medications.
- Alcohol use assessment (history; current consumption; AUDIT Score) (Appendix A).
- Perform single 12-lead ECG (Section 11.6).
- Draw and process blood samples for laboratory tests (Section 11.5):
 - Comprehensive metabolic panel (includes liver function tests [LFTs] as well as routine chemistry panel, glucose, CPK, magnesium)
 - Hematology (CBC)
 - Serology (HIV, HepB, HCV)
 - Coagulation (INR)
 - eGFR (CKD-EPI)
- Collect and process urine sample for laboratory tests (Section 11.5):

- Routine UA (dipstick)
- Pregnancy test (female subjects)
- Drug screen
- Perform complete physical examination including a neurological examination (Section 11.2).
- Draw blood for laboratory tests (Section 11.5):
 - PEth Test
 - Serum triglycerides concentration
 - o HbA_{1c}
 - o TSH, T4
- Record concomitant medications.
- Record any AEs.

If eligible, continue with the following screening assessments:

- Perform Fibroscan prior to MRI-PDFF to assess eligibility. (Section 10.3).
- Perform Ophthalmologic examination (Section 11.3).
- Perform MRI/MRI-PDFF (Section 10.1) with 30 days of Day 1 dosing

If eligible, schedule subject to return to for the Visit 2 / Day 1 to initiate HU6 dosing.

8.2.2 Baseline Visit 2 / Day 1

Subjects will have predose assessments at Visit 2 / Day 1 prior to administering the first dose of study drug. Subjects should present to this study visit in the fasted state (minimum 8-hour overnight fast).

The following predose procedures/assessments will be conducted on Day 1:

- Confirm eligibility against study inclusion/exclusion criteria.
- Medical history to determine if any changes have occurred since the Screening visit was performed.
- Draw and process blood samples for laboratory tests (Section 11.5):
 - Hematology (CBC)
 - Comprehensive metabolic panel (includes LFT as well as routine chemistry panel; glucose, CPK, magnesium)
 - o Glycated albumin
 - o hs-CRP
 - Low-density lipoprotein (LDL), very low-density lipoproteins (VLDL), high-density lipoprotein (HDL), FFA, total cholesterol, and triglycerides.
 - \circ ApoB and Lp(a)
 - o HOMA-IR includes glucose, insulin, and C-peptide

- Collect and process urine sample for laboratory tests (Section 11.5):
 - Routine UA (dipstick)
 - Pregnancy test (female subjects)
 - Drug screen
- Draw and process blood samples for PD assessments:
 - OWL metabolomics and OWL lipidomics (Section 10.4)
 - SomaScan proteomics (Section 10.5)
 - ELF assay (Section 10.6)
 - Exploratory biomarkers (Section 10.7)
- Draw and process blood sample for PK (Section 9.1).
- Perform targeted physical examination including a neurological examination (Section 11.2).
- Perform 12-lead ECG (Section 11.6).
- Measure and record vital signs including the InBody scale (Section 11.3).
- Record AEs or changes in medications since the Screening visit.

Administer study drug (Section 6.2.1) after completion of all predose assessments. Conduct the following **postdose procedures/assessments:**

- Draw and process blood samples for PK (Section 9.1) at approximately 2, 4, and 6 hours postdose.
- Measure and record vital signs (Section 11.3) prior to discharge.
- Record AEs and concomitant medications.

8.2.3 Visit 3 / Day 2

Subjects should present to this study visit in the fasted state (minimum 8-hour overnight fast).

The following predose procedures/assessments will be conducted on Day 2:

- Record AEs and concomitant medications.
- Measure and record vital signs including the InBody scale (Section 11.3).
- Collect and process blood sample for PK (Section 9.1).

Administer study drug (Section 6.2.1) after completion of all predose assessments. Conduct the following **postdose procedures/assessments:**

- Record AEs and concomitant medications.
- Dispense study drug.
- Dispense Daily Dosing Log.

8.2.4 Visit 4 / Day 7 (±1 day)

Subjects should present to this study visit in the fasted state (minimum 8-hour overnight fast).

The following predose procedures/assessments will be conducted:

- Collect and Review Daily Dosing Log.
- Measure and record vital signs including the InBody scale (Section 11.3).
- Perform 12-lead ECG (Section 11.6).
- Collect urine sample for pregnancy test (female subjects [Section 11.5]).
- Draw and process blood sample for PK (Section 9.1).
- Record AEs and concomitant medications.

After completing predose assessments:

- Administer study drug (Section 6.2.1) after completion of all predose assessments.
- Dispense study drug.
- Dispense Daily Dosing Log.

8.2.5 Visit 5 / Day 14 (±1 day)

Subjects should present to this study visit in the fasted state (minimum 8-hour overnight fast).

The following predose procedures/assessments will be conducted:

- Collect and Review Daily Dosing Log.
- Measure and record vital signs including the InBody scale (Section 11.3).
- Perform 12-lead ECG (Section 11.6).
- Record AEs and concomitant medications.
- Perform targeted physical examination including a neurological examination (Section 11.2).
- Collect urine sample for pregnancy test (female subjects [Section 11.5]).
- Draw and process blood sample for glycated albumin (Section 11.5).
- Draw and process blood sample for PK (Section 9.1).

Administer study drug (Section 6.2.1) after completion of all predose assessments. Conduct the following **postdose procedures/assessments:**

- Draw and process blood samples for PK (Section 9.1) at approximately 2, 4, and 6 hours postdose.
- Record AEs and concomitant medications.
- Measure and record vital signs (Section 11.3) prior to discharge.
- Dispense study drug.
- Dispense Daily Dosing Log.

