8.2.9.1 Visit 9a / Day 61 (±1 day)

On Study Day 61 (± 1 day), the following assessments will be conducted:

Subjects should present to this study visit in the fasted state (minimum 8-hour overnight fast).

The following predose procedures/assessments will be conducted:

- Collect and Review Daily Dosing Log.
- Draw and process blood samples for laboratory tests (Section 11.5):
 - Hematology (CBC)
 - Comprehensive metabolic panel (includes LFT as well as routine chemistry panel; glucose, CPK, magnesium)
 - o HbA_{1c}
 - Glycated albumin
 - hs-CRP
 - o LDL, VLDL, HDL, FFA, total cholesterol, and triglycerides
 - \circ ApoB and Lp(a)
 - HOMA-IR includes glucose, insulin, and C-peptide
- Collect and process urine sample for laboratory tests (Section 11.5):
 - Routine UA (dipstick)
 - Pregnancy test (female subjects)
 - Drug screen
- Draw and process blood samples for PD assessments:
 - OWL metabolomics and OWL lipidomics (Section 10.4)
 - SomaScan proteomics (Section 10.5)
 - ELF assay (Section 10.6)
 - Exploratory biomarkers (Section 10.7)
- Draw and process blood sample for PK (Section 9.1).
- Perform complete physical examination including a neurological examination (Section 11.2).
- Measure and record vital signs including the InBody scale (Section 11.3).
- Perform 12-lead ECG (Section 11.6).
- Record AEs and concomitant medications.
- Administer study drug (Section 6.2.1) if the visit occurs on Day 61. For those subjects whose visit occurs on Day 62, the last dose should be taken on Day 61, with no drug administered on Day 62.

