9 PHARMACOKINETIC ASSESSMENTS

9.1 Pharmacokinetic Sample Collection

Blood samples will be collected, and plasma samples prepared at the following times:

- On Day 1, 14, and 28: predose (trough) and approximately 2, 4, and 6 hours postdose.
- On Days 2, 7, 42, and 61: predose (trough) sample.
- One sample during Visit 10 or Early Termination.

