12.3.4 Safety Analysis

The safety analysis will be conducted on the FAS. Should there be any subjects that receive a treatment other the randomized treatment, the treatment as received will be used for safety presentations. AEs will be assessed for toxicity grade using NCI CTCAE (Version 5 or higher) and will be coded for summarization using Medical Dictionary for Regulatory Activities (MedDRA[®] Version 10.1 or higher). Concomitant medications will be coded using WHO Drug Dictionary (enhanced) Format C, 15 Aug 2005 or more recent updated version.

Treatment-emergent AEs will be summarized by SOC and preferred term, for each dose group (including placebo). Further summaries by seriousness, severity, and relationship to study drug may be conducted.

Laboratory measures will be summarized by treatment group and time-point both as absolute values and as change from baseline, with descriptive statistics summarizing each group and time point. Similar presentation will be used for vital signs and for ECG interval measurements, and changes from pre-treatment baseline. ECG intervals will be calculated from ECG/continuous ECG recordings at each time point.

A separate statistical analysis plan may be developed for exploratory evaluations of HU6 concentrations and QTcF.

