13.5 Electrocardiograms

Single 12-lead ECGs will be collected. For the quantitative variables RR, QRS, PR, QT, QTcF (QT interval corrected for heart rate by Fridericia's method), and heart rate, summary statistics (n, mean, standard deviation, minimum, median, and maximum) will be presented for the observed values at each time point, as described in Section 5.2, Summarization of Data. Summary statistics will also be presented for the change-from-baseline values to each postbaseline time point. In these displays, baseline will be defined as the last non-missing value prior to first dose of study medication.

The following results will be tabulated (n, %) by treatment group:

- Potential QTcF values of concern at any time post-baseline for:
 - o Increase from Baseline of >30 and <= 60 msec
 - o Increase from Baseline of > 60 msec

Post-baseline value > 500 msec

All ECG results will be displayed in subject listings for the safety population.

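### By schedule, all five on-treatment ECGs are predose, so the QTcF tables hold no systematic data from the 2 to 6 hours after dosing in which drug levels are sampled

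*Protocol*

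**What the plan says.** **Visit lists.** Protocol 8.2.5 (Day 14) opens its first list with "The following predose procedures/assessments will be conducted", and the line "Perform 12-lead ECG (Section 11.6" stands in that list. The list that follows dosing has "Draw and process blood samples for PK (Section 9.1) at approximately 2, 4, and 6 hours postdose" and a second set of vital signs, but no ECG. Sections 8.2.2 (Day 1), 8.2.4 (Day 7), 8.2.6 (Day 28), 8.2.7 (Day 42) and 8.2.9.1 (Day 61) also place the ECG in the predose list. In the Schedule of Assessments (8.1) the Day 1 postdose column is blank for ECG.

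**Last treatment visit.** Section 8.2.9.1 adds: "For those subjects whose visit occurs on Day 62, the last dose should be taken on Day 61, with no drug administered on Day 62". An ECG on Day 62 therefore also follows the last dose by about a day.

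**PK sampling.** Section 9.1 sets "On Day 1, 14, and 28: predose (trough) and approximately 2, 4, and 6 hours postdose". Days 2, 7, 42 and 61 have a trough sample only.

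**ECG type and analysis.** Protocol 11.6 and SAP 13.5 both specify single 12-lead ECGs. Protocol 11.6 also sets a 10-minute tolerance for an ECG that coincides with a blood sample. Protocol 12.3.4, however, states "ECG intervals will be calculated from ECG/continuous ECG recordings at each time point", and then "A separate statistical analysis plan may be developed for exploratory evaluations of HU6 concentrations and QTcF". SAP 13.5 counts "Potential QTcF values of concern at any time post-baseline for" three categories: an increase above 30 and up to 60 msec, an increase above 60 msec, and a value above 500 msec.

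**The concern.** Subjects are in clinic for at least 6 hours after the dose on Days 1, 14 and 28, and the protocol uses that time for PK and repeat vital signs. The ECG is the one cardiac safety measure left out. The SAP's outlier table is worded as if it covered the whole period after baseline, yet its scheduled on-treatment values all come from the end of a dosing interval.

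Two things are at stake. First, a clean outlier table could be read as reassurance about QTcF at the three doses when the hours after dosing were not systematically examined. Second, a concentration-QTcF evaluation, if undertaken, would have no scheduled pair at any postdose concentration, although those concentrations are being measured anyway. The primary efficacy analysis is not affected.

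**Working it through.** The plan gives no figure of its own to reproduce here. The check is a cross-tabulation of scheduled ECGs against scheduled PK samples, per subject, Days 1 to 61 (Protocol 8.1, 8.2.2 to 8.2.9.1 and 9.1).

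| Day | PK predose | PK at 2, 4, 6 h | ECG predose | ECG postdose |
|---|---|---|---|---|
| 1 | 1 | 3 | 1 (baseline) | 0 |
| 2 | 1 | 0 | 0 | 0 |
| 7 | 1 | 0 | 1 | 0 |
| 14 | 1 | 3 | 1 | 0 |
| 28 | 1 | 3 | 1 | 0 |
| 42 | 1 | 0 | 1 | 0 |
| 61 | 1 | 0 | 1 | 0 |
| Total | 7 | 9 | 6 | 0 |

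- PK samples: 7 + 9 = 16, of which 9 are postdose.
- ECGs: 6, less the Day 1 pre-treatment baseline, leaves 5 on treatment (Days 7, 14, 28, 42, 61).
- On-treatment ECGs paired with a trough sample: 5 of 5.
- Postdose PK samples paired with an ECG: 0 of 9.

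**Could other ECGs fill the gap?** Visit 10 (Day 73) comes after dosing has ended. The early termination ECG may fall up to 2 weeks after the last dose (7.4.1) and is not timed to a dose. An unscheduled ECG for a safety concern (Section 8, introduction) could fall postdose, but it would be prompted by an event and so is not systematic. No continuous recording appears in the schedule, the visit lists, 11.6 or the SAP. Continuous telemetry appears only in 6.5, for overdose or toxicity.

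**How far below peak is trough?** The documents supplied give no Tmax or half-life for HU6, DNP or M1, so this can only be bracketed. Assume one-compartment decline, a peak at 4 hours and a trough at 24 hours. Then trough/peak = 2^(−(24 − 4)/t½) = 2^(−20/t½):

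| Assumed half-life (h) | Trough/peak |
|---|---|
| 6 | 0.10 |
| 12 | 0.31 |
| 24 | 0.56 |
| 48 | 0.75 |

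Moving the assumed peak between 2 and 6 hours changes these to 0.08–0.13, 0.28–0.35, 0.53–0.59 and 0.73–0.77. The unknown half-life dominates.

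**After the change proposed below.** On-treatment ECGs stay at 5. Two become postdose (Days 14 and 28), so postdose pairs rise from 0 to 2 per subject and trough pairs fall from 5 to 3.

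**The case against.** The best case for the plan is that this is an exploratory Phase 2a trial. Its ECG endpoint is descriptive safety monitoring, and no objective claims to exclude a QT effect. The concentration-QTcF plan is optional. The Introduction, which would hold earlier clinical experience and the dose rationale, is not in the text supplied, so postdose ECGs may already exist from other studies. If the analyte that matters has a long half-life, trough ECGs capture most of the exposure.

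The threefold dose range also helps. Assuming dose proportionality and the ratios above, the 450 mg trough is 3 × 0.31, 3 × 0.56 or 3 × 0.75, about 0.9, 1.7 or 2.2 times the 150 mg peak, at half-lives of 12, 24 or 48 hours. Trough pairs could therefore inform a slope.

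Much of this stands, and it limits the weight of the point. It does not close the gap. Trough data do not reach the 450 mg peak, and at a 6-hour half-life the 450 mg trough is only about 3 × 0.10 = 0.3 of the 150 mg peak. Labelling the tables as predose would prevent a misreading but would still leave the postdose hours unobserved.

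A reader might infer three stronger things that the documents do not support:
- That postdose QTcF can never be observed. Unscheduled ECGs are possible, and follow-up and early termination ECGs also enter the outlier table.
- That the protocol acknowledges a QT signal for HU6 at the study doses. The QT exclusions and Appendix B concern subjects' own risk and other drugs, and 6.5 concerns overdose or toxicity.
- That a given number of msec is being missed. No effect size, peak time or half-life is available to support such a figure.

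**Conclusion.** The point holds as a statement about the schedule. None of the five scheduled on-treatment ECGs falls after that day's dose, and none of the nine postdose PK samples has an ECG beside it. The SAP 13.5 tables, and any concentration-QTcF evaluation, would contain no systematic on-treatment QTcF data from 2 to 6 hours postdose, while the wording of the outlier table suggests broader coverage.

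The counts rest on no assumption. The consequence does: under the one-compartment, 4-hour-peak assumption, trough could be anywhere from about 10% to 75% of peak, so the documents cannot show whether little or most of an exposure-driven effect would be missed. Separately, the continuous recordings named in Protocol 12.3.4 match no procedure and conflict with 11.6 and SAP 13.5. Overall this is a worthwhile, low-cost improvement, not a flaw that undermines the trial.

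**What to change.** 1. **Protocol 8.1, 8.2.5 and 8.2.6.** On Days 14 and 28, record the already scheduled single ECG at one prespecified existing postdose PK time. Use the same time in all arms, chosen from the sponsor's own PK data. Apply the 10-minute tolerance in 11.6, and take the ECG before any meal where possible, since 6.2.1 requires fasting only until 1 hour after the dose. Keep the predose ECGs on Days 1, 7, 42 and 61.
2. **SAP 13.5.** Present QTcF change and outlier counts by time relative to dose, and read the postdose changes against placebo.
3. **Protocol 12.3.4.** Reconcile the reference to continuous recordings with the single 12-lead ECGs in 11.6 and SAP 13.5.

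**Cost.** No extra ECG, visit or staff: two existing ECGs are re-timed and one set of tables is split. In exchange, there are two fewer trough ECGs, with none between Day 7 and Day 42. Postdose values are compared with a fasted predose Day 1 baseline, so time of day and food can shift within-subject changes. The placebo arm helps with the between-group reading but does not correct individual outlier counts. A single postdose time may also miss the peak.
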